#### *CSF Measurements*

The quick CSF method, implemented in a 10 alternative forced-choice digit identification task, was used to assess the contrast sensitivity function. Stimuli were displayed on a gamma-corrected 46 inch LCD monitor (Model: NEC LCD P463) with a 1920×1080 pixel resolution, 50 cd/m^2 mean luminance and 60 Hz vertical refresh rate. Observers viewed the display monocularly from a distance of 4 m in a dark room. For each trial, they were asked to verbally report the identities of three digits presented on the screen to the experimenter, who used the computer keyboard to enter their responses. The stimuli disappeared after all the responses were entered. Observers were given the option to report “I don’t know” upon which the response

was coded as incorrect. No feedback was provided. All three responses were used to update the posterior distribution of the CSF parameters, which in turn was used to adaptively choose the most informative combination of spatial frequency and contrast for the next trial. A new trial started 500 ms after the responses. There were 30 trials in approximately 5 min. The quick CSF data were scored to generate the cutoff spatial frequency, defined as the spatial frequency corresponding to a perceptual sensitivity of 1, and the area under the log CSF (AULCSF), a summary measure of the window to spatial vision.

### **Statistical Analysis Plan:**

Data would present as means  $\pm$  standard deviations. Between group t-test would be used for statistical comparisons of the CSF results, including cutoff SF and AULCSF between the astigmatism group and the control group. A multiple linear regression analysis would be performed to investigate the relation between the AULCSF and the lens power of astigmatism. Statistical analyses were performed using SPSS version 17.0 (SPSS, Inc., Chicago, IL, USA), and p values of  $< 0.05$  would be considered statistically significant.

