**Background and Objective(s):**

Keratoplasty, also known as corneal transplantation, is a surgical procedure in which a damaged or diseased cornea is replaced entirely (penetrating keratoplasty) or partially (lamellar keratoplasty) by a donated corneal graft. Post-keratoplasty astigmatism is multifactorial in its etiology, in which the preoperative factors involve the age and health of donor tissue, recipient pathology, the intraoperative factors include trephine quality, graft size, wound apposition and suturing technique and suture material and the postoperative factors cover wound healing, postoperative drugs, inflammation, corneal vascularization, rejection.

The contrast sensitivity function (CSF) provides a comprehensive measure of the visual system which has been used to characterize spatial vision deficits in many visual disorders such as amblyopia, multiple sclerosis, glaucoma, retinitis pigmentosa, as well as autism spectrum disorder. Although some studies have reported the contrast sensitivity function of keratoplasty patients, few has documented the CSF in different spatial frequencies as well as its relationship between the life quality. To our knowledge, the current study would be the first case series to inquiry the contrast sensitivity function in the keratoplasty patients with quick CSF, as well the relationship between visual quality and life quality.

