**Design:**

All participants would undergo an ophthalmic examination that included slit-lamp biomicroscopy , visual acuity, corneal topography, contrast sensitivity measurements, 9-SF life quality questionnaire and fundus examination. Then the normal group would be covered by positive spherical lens of 1.0D to 6.0D to repress the BCVA to 0.1 to 0.9 respectively to compare the visual functions with the keratoplasty patients on the same visual acuity.

**Methods:***Subjects and Inclusion Criteria*

This observational, cross-sectional, non-consecutive case study would be conducted with patients who have accepted keratoplasty and healthy subjects who visited the Corneal Clinic of Zhongshan Ophthalmic Center, Guangzhou, China. The research was performed according to the tenets of the Declaration of Helsinki. The study protocol was approved by the Zhongshan Ophthalmic Ethical Committee. All subjects provided informed consent after receiving both written and verbal explanations of the nature and intent of the study.

The Inclusion Criteria for keratoplasty patients are: 1) Accept the corneal transplantation based on the clinical diagnosis of ocular surface disease; 2) more than 7 and less than 60 years old; 3) absence of other ocular disorders and no history of eye surgery and other systemic diseases. And the exclusion Criteria are: 1) less than 7 or more than 60 years old; 2) with the history of eye surgery and other systemic diseases.

All participants underwent an ophthalmic examination that included slit-lamp biomicroscopy , visual acuity, corneal topography, contrast sensitivity measurements, 9-SF life quality questionnaire and fundus examination. Then the normal group would be covered by positive spherical lens of 1.0D to 6.0D to repress the BCVA to 0.1 to 0.9 respectively to compare the visual functions with the keratoplasty patients on the same visual acuity.

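### The plan's only group test, an unpaired t-test, does not say how the acuity matching that motivates the blurred controls enters the analysis

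*Combined protocol and SAP*

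**What the plan says.** The Design section, repeated under Methods, states that "the normal group would be covered by positive spherical lens of 1.0D to 6.0D to repress the BCVA to 0.1 to 0.9 respectively" and gives the purpose: "to compare the visual functions with the keratoplasty patients on the same visual acuity".

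The Statistical Analysis Plan has two inferential analyses.

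- **Group comparison:** "Between group t-test would be used for statistical comparisons of the CSF results, including cutoff SF and AULCSF". No covariate, pairing, stratum or subject term is named, and nothing says whether blurred or unblurred control readings are used.
- **Regression:** "A multiple linear regression analysis would be performed to investigate the relation between the AULCSF and the lens power of astigmatism". This names neither group nor visual acuity, so it does not supply the same-acuity comparison.

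The patient group also changes name. The Background refers to "the first case series to inquiry the contrast sensitivity function in the keratoplasty patients with quick CSF", while the analysis compares measurements "between the astigmatism group and the control group".

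**The concern.** The same-acuity comparison is the stated reason for blurring the controls, yet nothing in the analysis section carries it through. What the t-test estimates, and how it behaves, depends on a choice the plan leaves open.

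- **One acuity-matched reading per control** (closest to the Design section). Acuity spread is common to both groups and cancels from the difference, but the unpaired test leaves it in the error term. The test is valid but conservative, and can miss a real deficit at equal acuity.
- **Several lens readings per control, pooled.** Readings from one person are treated as independent, and the control mean follows the mix of lenses rather than the patients' acuity mix. A deficit could be reported that comes from clustering or from an acuity gap.
- **A separate t-test at each acuity level.** The matching is used, but strata are small, tests are multiple, and the same controls may serve at several levels.
- **Unblurred readings.** Acuity would be confounded with keratoplasty. This is the use least consistent with the Design section.

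**Working it through.** The plan states no sample size, power, SD or effect size, so there is no figure to reproduce. The check has two parts: setting the sections side by side, as above, and an illustration on assumed inputs.

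**Inputs.** From the documents: blurred acuity 0.1 to 0.9; significance level 0.05 (two-sided assumed). Assumed: n = 30 per group; AULCSF SD at fixed acuity s = 0.20; acuity spread evenly over decimal 0.1, 0.2, …, 0.9; slope b = 0.25, 0.5 or 1.0 AULCSF units per logMAR; true difference 0.15; 75% of s² between subjects.

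**Acuity spread.** logMAR = −log10(decimal) gives 1.000, 0.699, 0.523, 0.398, 0.301, 0.222, 0.155, 0.097, 0.046. The mean is 0.382 and the variance V is 0.0867.

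**Reading 1: one matched reading per control.** Because acuity cancels, the true SE of the difference is s·√(2/n) = 0.20·√(2/30) = 0.0516. The unpaired test instead uses an SE of √[2(s² + b²V)/n].

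| Slope b | SE used | SE used / true SE | Effective cut-off (2.0017 × ratio) |
|---|---|---|---|
| 0.25 | 0.0550 | 1.066 | 2.133 |
| 0.5 | 0.0641 | 1.242 | 2.486 |
| 1.0 | 0.0919 | 1.780 | 3.563 |

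The standardised effect is 0.15/0.0516 = 2.905. Approximate power is Φ(2.905 − cut-off), which gives 78%, 66% and 26%. A paired t-test (29 df, critical value 2.045) gives Φ(2.905 − 2.045) = 80% at every slope. Simulation (20,000 replicates), which does not rely on the normal approximation, gives:

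| Slope b | Unpaired: false positives | Unpaired: power | Paired: power | Acuity-adjusted: power |
|---|---|---|---|---|
| 0.25 | 3.7% | 78% | 80% | 82% |
| 0.5 | 1.7% | 66% | 80% | 82% |
| 1.0 | 0.1% | 27% | 80% | 81% |

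The paired and adjusted tests hold about 5% false positives. Across n = 20 to 50 and SD 0.15 to 0.30, the unpaired test loses 0–4, 1–22 and 20–71 power points against the paired test at the three slopes.

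**Reading 2: k lens readings per control, pooled as independent.** With T = s² + b²V, the test uses variance T(1/n + 1/(nk)). The true variance is T/n + 0.75s²/n + (0.25s² + b²V)/(nk). For k = 6 and b = 0.25, T = 0.0454. The variance used is 0.0454 × (1/30 + 1/180) = 0.00177, and the true variance is 0.00260. The effective cut-off is therefore about 1.63 and false positives about 10%. Simulation (10,000 replicates, k = 6) gives the rates below for the three slopes.

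| Acuity mismatch (logMAR) | b = 0.25 | b = 0.5 | b = 1.0 |
|---|---|---|---|
| 0 | 11% | 8% | 6% |
| 0.05 | 12% | 12% | 13% |
| 0.15 | 20% | 36% | 56% |

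Averaging each control's readings first removes the clustering but not the mismatch. At 0.15 logMAR with k = 6 it still gives 10%, 26% and 51%.

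**Reading 3: separate tests by level.** With nine levels, 30 patients leave 30/9 ≈ 3.3 per level. Two outcomes make 18 tests. If the nine tests of one outcome were independent, the chance of at least one false positive would be 1 − 0.95⁹ = 37%. Reused controls would make the tests dependent, so this is only a guide.

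**Check on the remedy.** A random-intercept model with logMAR acuity and age, with 2, 3 or 6 control readings, held 4.1–5.7% false positives and 83–85% power when both groups shared one slope. In a simplified version (known variances, no age term, 3 or 6 control readings, no true difference at the patients' average acuity), unequal slopes raised false positives. Patient/control slopes of 0.25/0.75 gave 7–8%, and 0.25/1.0 gave 11–12%. With patient variance doubled (slope 0.5), the random-intercept model gave 5.3–6.6%.

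**The case against.** The strongest reply is that the lack of adjustment is inferred from silence. The analysis section does not forbid feeding matched readings into the t-test, or running it within acuity levels, and the list of blur levels in the Design section makes the second plausible. A reader might infer that the planned test discards the matching, or that its result will be biased. The documents do not support either. With one matched reading per control the matching is used and only precision is lost, and a within-level test uses it directly. This part of the reply stands.

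A reader might also take unblurred controls as the expected analysis. On the same assumptions that would give false-positive rates of 41%, 90% and over 99%. It is the use least consistent with the Design section, so those figures should not be read as the size of the problem.

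The size is driven by assumptions, which also stands. At slope 0.25 with matched readings the loss is 0–4 power points. The simulations concern AULCSF only; cutoff SF was not simulated. The label point is minor, since the Background discusses astigmatism after keratoplasty, which explains the term.

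What the reply does not remove is that the plan names a specific test which is conservative, clustered, fragmented or confounded depending on an unstated choice. A paired or acuity-adjusted analysis of readings the design already calls for would do better.

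**Conclusion.** The point holds as a gap between design and analysis: the same-acuity comparison is the purpose of the blurring, and the Statistical Analysis Plan does not specify how it enters the only group test. It should be fixed. Confidence in the gap is high, because it rests on the text. Confidence in its size is low, because sample size, SD, acuity slope, lenses per control and any acuity mismatch are all assumed.

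Under the reading closest to the Design section, the consequence is lost power: about 78%, 66% and 27% against 80% for a paired test in the base case. If AULCSF depends only weakly on acuity, that loss is small. Inflated false positives arise only if several readings per control are pooled as independent, or if the control readings differ from the patients' in acuity.

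**What to change.** - **State the data.** Lens-blurred, acuity-matched control readings enter the same-acuity comparison, limited to the acuity range where both groups have readings. Report the unblurred comparison, and patients outside that range, descriptively.
- **Replace the unpaired t-test.** If each control gives one matched reading, use a paired t-test or a linear model with group and logMAR acuity. If controls give several readings, use the same model with a random intercept per subject. Apply it to both AULCSF and cutoff SF. Age adjustment is optional.
- **Check the assumptions.** State that the model assumes one acuity slope for both groups, and test this with a group-by-acuity term. If slopes differ, report the group difference at stated acuity levels. Check linearity with a quadratic term, and equal variance by refitting with separate group variances.
- **Record acuity with each CSF result,** measured through the lens for controls.
- **Use one name for the patient group.**

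The cost is revised wording and modest extra analysis, plus reliance on the model assumptions above. No new visits are needed if acuity through each lens was recorded with its CSF reading. The documents do not say that it was, and parts are written in the past tense, so this should be confirmed first.

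### The only group test of cutoff SF and AULCSF is a t-test with no age term, in a non-randomised study of patients aged 7 to 60 with no stated age matching

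*Combined protocol and SAP*

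**What the plan says.** The Statistical Analysis Plan gives one group comparison: "Between group t-test would be used for statistical comparisons of the CSF results". It covers "cutoff SF and AULCSF between the astigmatism group and the control group" and names no covariate. The Design and Methods text describes only keratoplasty patients and healthy or normal subjects, so reading the SAP's astigmatism group as the keratoplasty group is an inference.

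The only other analysis is this: "A multiple linear regression analysis would be performed to investigate the relation between the AULCSF and the lens power of astigmatism". It omits cutoff SF and names neither group nor age.

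Under Methods (Subjects and Inclusion Criteria), the study is an "observational, cross-sectional, non-consecutive case study". Patients must be "more than 7 and less than 60 years old". Controls are "healthy subjects who visited the Corneal Clinic". The inclusion list is headed for keratoplasty patients. The exclusion list repeats the age limits without saying which group it governs.

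The Design section says that "the normal group would be covered by positive spherical lens of 1.0D to 6.0D", the aim being "to compare the visual functions with the keratoplasty patients on the same visual acuity". Age matching, age stratification and an age covariate appear nowhere.

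**The concern.** Nothing in the design balances age between the groups. There is no randomisation, enrolment is not consecutive, and the eligible patient range spans 60 - 7 = 53 years. Even if the exclusion list also applies the age limits to controls, sharing a 53-year window is not matching.

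Two conditions must both hold for this to bias the result:

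1. The groups' age distributions differ, in mean or in spread.
2. Age affects cutoff SF or AULCSF among people with the same visual acuity.

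If both hold, an unadjusted t-test reports part of the age difference as a group effect, in either direction, and no other planned group analysis would show it. The lens-power regression cannot, because it does not compare the groups. Even if an unnamed age term sits behind the word multiple, the patient-control contrast stays unadjusted.

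**Working it through.** **No plan figure to reproduce.** The documents give no sample size, SD, effect size, observed ages or age effect. Every input below is therefore assumed, apart from the 7-60 range and the 0.05 significance level (taken as two-sided). All cases have 30 per group and no true group effect, so a valid test rejects in 5% of studies.

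**1. Straight-line age effect.** Let r be the age-outcome correlation and d the gap in mean age, in age SDs. The spurious group difference is r × d outcome SDs. With n = 30 per group the noncentrality is r × d × √(n/2) = r × d × √15, on 58 degrees of freedom. If ages were uniform over 7-60, one age SD would be 53/√12 = 15.3 years.

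| r | d | Spurious difference (SD) | Noncentrality | t-test false-positive rate |
|---|---|---|---|---|
| 0.2 | 0.33 | 0.066 | 0.26 | 5.7% |
| 0.3 | 0.5 | 0.15 | 0.58 | 8.8% |
| 0.45 | 1.0 | 0.45 | 1.74 | 40.3% |

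In simulation of the same three cases, a model with age and age squared gave 5.4%, 5.1% and 5.1%.

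**2. Inverted-U age effect** (scores lower at both ends of the range). Take the effect as -(age - 33.5)², standardised over a uniform 7-60 distribution and explaining a share R² of the variance. The SD of (age - 33.5)² is 26.5² × √(4/45) = 209.4. For a group uniform on [a, b], the mean of (age - 33.5)² is (b - a)²/12 + (midpoint - 33.5)². The spurious difference is the gap between the two group means, divided by 209.4 and multiplied by √R².

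- 7-60 against 20-47 (both with mean age 33.5): (234.1 - 60.75)/209.4 = 0.83, so 0.83 × √R².
- 7-60 against 18-60: (234.1 - 177.25)/209.4 = 0.27, so 0.27 × √R².
- 22-60 against 7-45 (means 15 years apart): 176.6 - 176.6 = 0, so no bias.

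Simulated false-positive rates at R² = 0.04 / 0.09 / 0.20 (5,000 runs, Monte Carlo standard error about 0.3 points near 5%):

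| Ages, patients v controls | t-test | Linear age term | Age + age squared |
|---|---|---|---|
| 22-60 v 7-45 | 5.0 / 5.4 / 4.7% | - | - |
| 7-60 v 18-60 | 5.1 / 5.9 / 8.0% | 5.3 / 6.7 / 9.7% | 4.7 / 4.8 / 5.0% |
| 7-60 v 15-52 | 7.0 / 10.8 / 16.9% | - | 5.3 / 5.2 / 5.4% |
| 7-60 v 20-47 | 10.2 / 15.7 / 31.2% | 9.7 / 14.9 / 29.4% | 5.2 / 4.7 / 5.0% |

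Equal mean ages therefore do not guarantee a fair comparison, a 15-year gap can be harmless, and under this shape a straight-line age term does not remove the bias.

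**3. Dependence on shape.** If age matters only in childhood and levels off at 15, the 7-60 against 20-47 case gives 5.0%, 6.9% and 10.0% for the t-test, about a third of the inverted-U rate at R² = 0.20.

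**4. Precision.** The standard error of the group difference with age and age squared, divided by that of the t-test, was 0.997 / 0.971 / 0.910 when both groups were 7-60, 1.152 / 1.135 / 1.095 for 7-60 against 20-47, and at most 1.224 (7-40 against 18-60, R² = 0.04).

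**The case against.** The strongest reply is that the groups are to be compared at equal acuity, so much of any age effect may already be gone. That stands in part: whatever age does through acuity is at least partly removed, and the remainder may be smaller than a raw age effect. But comparing contrast sensitivity at equal acuity presumes that it carries information beyond acuity, so equal acuity cannot be assumed to remove every age effect. The task also has subjects report digits aloud over 30 trials, with a don't-know answer scored as wrong; that is a plausible but unproven route for an age effect in children.

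Second, no imbalance is shown, and the large rates need strong assumptions. This stands. The 40% figure needs r = 0.45 together with a full-SD age gap, and nothing in the documents confines controls to 20-47. An easy imbalance to imagine, some children among the patients and only adult controls, gives 5-8% under the inverted U.

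Third, a pooled model could alter the planned contrast by assuming that acuity acts linearly. This also stands, and is why acuity should enter as a factor or stratum.

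Finally, the study calls itself a case series and states no formal hypothesis or primary endpoint. That limits the weight of the point but does not remove it, since the SAP still sets a significance threshold for the group tests.

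**Conclusion.** The gap is real: the only group test of cutoff SF and AULCSF has no age term, and nothing stated in the design balances age. Whether it biases this study is conditional on differing age distributions and on an age effect at a given acuity, neither of which the documents establish.

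A reader might infer that the comparison is confounded by age, or that a false-positive rate of 30-40% is to be expected. The documents support neither. They show missing protection against a plausible confounder, with unknown size and direction; a rate near 5% is as compatible with them as a large one. Nor do they show that the whole raw age effect would reach the result, given the same-acuity comparison.

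This is a change the sponsor should make, held with medium confidence. It rests on reading the astigmatism group as the keratoplasty group; on any reading of that label, the test has no age term and the groups are not randomised. Repeated lens measurements on the same control are a separate matter and form no part of this point.

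**What to change.** Replace the t-test with a prespecified linear model, one for cutoff SF and one for AULCSF, containing group, age and age squared. Fit it within the planned same-acuity comparison, with acuity level as a categorical or stratifying factor rather than a straight-line term. State which participants form the astigmatism group. Recruiting controls of similar age is an optional addition.

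The cost is a short SAP change and no new data, assuming control age is recorded; the documents make age an explicit eligibility item only for patients. Acuity is already in the stated examination. Age uses two degrees of freedom, and an acuity factor uses one fewer than its number of levels. In the simulations, which had no acuity factor, the age terms changed the standard error by a factor of about 0.91 to 1.22, so the interval may narrow slightly when ages are alike and widen when they differ markedly.
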